10.15 APPENDIX 15: PROTOCOL AMENDMENT HISTORY

Not applicable.

# **VERSION HISTORY**

This statistical analysis plan (SAP) for Study ACT16444 is based on the protocol dated 19-Apr-2021. The first participant was enrolled in the dose escalation part on 21-Nov-2021. This SAP is approved before the primary analysis of Objective Response Rate (ORR).

			Defferente
SAP version	Approval Date	Changes	Rationale
1	17-Jul-2023	Estimands attributes have been updated for efficacy endpoints.	Corrections to align with ICH E9 (R1) definitions.
		Definition of DLT-evaluable population (for Part 1) has been updated.	Clarification on the definition.

## Major changes in statistical analysis plan

# 1 INTRODUCTION

# 1.1 STUDY DESIGN

This is a Phase 2, open-label, multicenter, single-arm study to confirm the recommended dose, safety, efficacy (antitumor activity), and pharmacokinetics (PK) of tusamitamab ravtansine combined with ramucirumab in participants previously treated for gastric or gastroesophageal adenocarcinoma with CEACAM5-positive tumors.

The study will comprise 2 parts: Part 1 (Safety run-in) to assess the tolerability and to confirm the recommended dose (RD) of tusamitamab ravtansine in combination with ramucirumab; and Part 2, to assess the antitumor activity of tusamitamab ravtansine in combination with ramucirumab.

The screening phase will be performed only in prescreened participants determined to be CEACAM5-positive by immunohistochemistry (IHC) assessment.

Approximately 32 to 38 participants will be treated from approximately 21 sites to achieve a total of 32 participants treated at the RD and evaluable for activity.

The cycle duration is 14 days. The median expected duration of study per participant is estimated at 34 weeks (up to 4 weeks for screening, a median of 18 weeks for study intervention administration, a median of 12 weeks for end-of-treatment (EOT) assessments, and the safety follow-up visit).

Treatment allocation will be performed using interactive response technology (IRT). After being screened, eligible participants will receive tusamitamab ravtansine combined with ramucirumab until documented disease progression, unacceptable toxicity, new anticancer therapy initiation, death, or the participant's or Investigator's decision to stop the treatment.

This will be a 2-part study.

• Part 1 (safety run-in): participants will receive ramucirumab 8 mg/kg followed by tusamitamab ravtansine at 170 mg/m^2 at Day 1 Cycle 1, and ramucirumab 8 mg/kg followed by tusamitamab ravtansine 100 mg/m^2 at Cycle 2 Q2W in all subsequent cycles. In the case that it is decided to reduce the initial loading dose of tusamitamab ravtansine to Dose Level (DL)-1 (Table 1), a tusamitamab ravtansine loading dose of 150 mg/m^2 will be administered to participants at Day 1 of Cycle 1.

Dose Level (DL)	Tusamitamab revtansine	Ramucirumab
Starting dose	170 mg/m  Q2W Cycle 1;	8 mg/kg Q2W
-	100 mg/m  Q2W Cycle 2 and thereafter	
Minus -1 (DL-1)	150 mg/m  Q2W Cycle 1;	8 mg/kg Q2W
	100 mg/m  Q2W Cycle 2 and thereafter	

Table	1 -	Dose	levels	in	safety	run-in	nart
lable		D036	level2		Salety	run-m	μαπ

DL-1 = dose level -1; Q2W = every 2 weeks

• Part 2: Participants enrolled in the dose expansion part will receive SAR408701 at the RD determined at the end of the safety run-in (Part 1).

Property of the Sanofi group - strictly confidential

Page 6

# 1.2 OBJECTIVES AND ENDPOINTS

#### Table 2 - Objectives and endpoints

	Objectives	Endpoints
Prima	ry	
•	Part 1: to confirm the recommended tusamitamab ravtansine loading dose Q2W when given in combination with ramucirumab in advanced gastric or gastroesophageal junction (GEJ) adenocarcinoma population	
 
Part 1: Incidence of study drug related dose-limiting toxicities (DLTs) at Cycle 1 and Cycle 2 (C1D1 to C2D14)
 

•	Part 2: To assess the antitumor activity of tusamitamab ravtansine loading dose Q2W in combination with ramucirumab in advanced gastric or GEJ adenocarcinoma	• Part 2: Objective response rate (ORR), defined as the proportion of participants with confirmed complete response (CR) or partial response (PR) as best overall response (BOR) per Response Evaluation Criteria in Solid Tumors (RECIST) 1.1
Secon	dary	
•	To assess the safety and tolerability of tusamitamab ravtansine loading dose Q2W in combination with ramucirumab	
 
Incidence of treatment-emergent adverse events (TEAEs), serious adverse event (SAEs), and laboratory abnormalities according to the National Cancer Institute (NCI) Common Terminology Criteria for Adverse Events (CTCAE) V5.0
 

•	To assess the durability of the response to treatment with tusamitamab ravtansine loading dose Q2W in combination with ramucirumab	
 
Duration of response (DOR), defined as the time from first documented evidence of CR or PR until progressive disease (PD) determined per RECIST 1.1 or death from any cause, whichever occurs first
 

•	To assess progression-free survival (PFS) of tusamitamab ravtansine loading dose Q2W in combination with ramucirumab	
 
Progression-free survival, defined as the time from the first investigational medicinal product (IMP) administration to the date of the first documented disease progression or death due to any cause, whichever comes first
 

•	To assess the disease control rate (DCR) of tusamitamab ravtansine loading dose Q2W in combination with ramucirumab	• Disease control rate, defined as the proportion of participants with confirmed CR or PR or stable disease (SD) as BOR per RECIST 1.1
•	To assess the PK of tusamitamab ravtansine loading dose Q2W and ramucirumab when given in combination	Pharmacokinetic parameters of tusamitamab ravtansine and ramucirumab
•	To assess the immunogenicity of tusamitamab ravtansine loading dose Q2W when given in combination with ramucirumab	
 
Incidence of antitherapeutic antibodies (ATAs) against tusamitamab ravtansine
 

Explo	ratory	
•	To explore the circulating carcinoembryonic antigen (CEA) as a potential biomarker for activity and to evaluate circulating CEA levels at prescreening	
 
Circulating CEA at prescreening, screening, during the treatment period and during the follow-up period
 

events, SAEs = serious adverse events.

Property of the Sanofi group - strictly confidential

Page 7

### 1.2.1 Estimands

The primary estimand defined for the primary efficacy endpoint is summarized in Table 3. More details are provided in Section 3.

Statistical Analysis Plan SAR408701-ACT16444 - tusamitamab ravtansine 17-Jul-2023 Version number: 1

#### Table 3 - Summary of primary estimand for primary efficacy endpoint

Endpoint	Estimands				
Category (estimand)	Endpoint	Population	Intercurrent event(s) handling strategy	Population-level summary (Analysis and missing data handling)	
Primary efficacy object adenocarcinoma	tive: To assess the antitum	or activity of tusamitam	ab ravtansine loading dose Q2W in combination with	ramucirumab in advanced gastric or GEJ	
Primary endpoint (primary estimand for Part 2)	Confirmed objective response (confirmed CR or PR as BOR) as per RECIST 1.1	All-treated population at the recommended tusamitamab ravtansine loading dose	Regardless of IMP discontinuation (treatment policy strategy) "While not initiating further systemic anticancer therapy" strategy)	ORR, defined as the rate of participants with confirmed objective response, and 2-sided 95% confidence interval (CI) using the Clopper-Pearson method. In the absence of confirmed objective response, participants will be considered as nonresponders, whatever the reason (including participants with nonevaluable BOR).	

# 2 ANALYSIS POPULATIONS

The following populations for analyses are defined:

Population	Description		
Prescreened	All participants who signed the prescreening informed consent for CEACAM5 assessment of their biopsy.		
Screened	All participants who signed the screening informed consent for study participation.		
Enrolled	Participants from screened population who have been allocated to intervention regardless of whether the intervention was received or not.		
All-treated	All enrolled participants exposed to the study treatment, regardless of the amount of treatment administered. All safety analyses will be performed on this population, which is also the primary population for analysis of all efficacy parameters.		
DLT-evaluable (Part 1)	All enrolled participants who received 2 cycles with at least 80% of the intended dose for both tusamitamab ravtansine and ramucirumab at each of the first 2 infusions. Any participant who experienced a DLT during that period will also be DLT-evaluable.		
Activity	All-treated participants who have measurable disease at study entry and at least 1 postbaseline evaluable tumor assessment. Participants with no postbaseline evaluable tumor assessment but with an early clinical progression or who died from disease progression will also be included in this set. This population is the secondary population for analysis of efficacy parameters.		
Pharmacokinetic (PK)	All participants from the all-treated population with at least 1 postbaseline PK concentration (whatever the cycle and even if dosing is incomplete) with adequate documentation of dosing and sampling dates and times.		
ATA	All participants from the all-treated population with at least 1 postbaseline ATA result (negative, positive, or inconclusive).		
Population without trial impact	All treated participants:		
(disruption) due to COVID-19	
 
without any critical or major deviation related to COVID-19
 
		
	
 
and who did not permanently discontinue treatment due to COVID-19
 
		
	
 
and who did not permanently discontinue study due to COVID-19.
 
		

Table 4 - Populations	for analyses
-----------------------	--------------

In practice, a participant will be included in the enrolled population if the question "Will the subject continue in the treatment phase?" has been answered "Yes" in the "Completion of screening phase" e-CRF page.

In practice, a participant will be included in the DLT-evaluable population (applicable to Part 1 only) if a "Dose Limiting Toxicities" e-CRF page has been filled in at the end of Cycle 1 and at the end of Cycle 2 (or Cycle 1 only if participant did not receive Cycle 2 because of a DLT). This includes any participant followed up to the end of the DLT observation period, or having experienced a DLT before the end of the DLT observation period and validated by the Study Committee. A participant with an overdose (defined as a dose received at least 30% above the intended dose) of tusamitamab ravtansine or ramucirumab at any of the 2 first infusions will be excluded from the DLT-evaluable population.

Statistical Analysis Plan SAR408701-ACT16444 - tusamitamab ravtansine 17-Jul-2023 Version number: 1

Participants exposed to study intervention before or without being enrolled will not be considered enrolled and will not be included in any analysis population. The safety experience of these participants will be reported separately. Enrolled participants for whom it is unclear whether they took the study intervention will be considered as exposed and will be included in the all-treated population.

For any participant enrolled more than once, only the data associated with the first enrollment will be used in any analysis population. The safety experience associated with any later enrollment will be reported separately.

In practice, participants whose BOR is nonevaluable due to minimum criteria for SD duration not met (ie, overall response of SD and the minimum duration, defined as 0.75 x duration between the first IMP intake and the first planned tumor assessment is not met) and there is no subsequent evaluable tumor assessment, or documented PD after two or more non-evaluable tumor assessments (ie, overall response of PD and the time between the date of first IMP intake and the documentation of PD is greater than the theoretical planned date of the second tumor assessment) will be considered as not evaluable for the activity population.

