In Part 1, participants will receive ramucirumab 8 mg/kg followed by tusamitamab ravtansine at 170 mg/m² (150 mg/m²) at Day 1 Cycle 1, and ramucirumab 8 mg/kg followed by tusamitamab ravtansine 100 mg/m² at Cycle 2 and Q2W in all subsequent cycles. In the case that it is decided to reduce the initial loading dose of tusamitamab ravtansine to DL-1 (Table 1), a tusamitamab ravtansine loading dose of 150 mg/m² will be administered to participants on Day 1 of Cycle 1.

Table 1 - Dose levels for Part 1 (safety run-in)

[figure not shown]
Dose level (DL)	Tusamitamab ravtansine	Ramucirumab
Starting dose	170 mg/m ² Q2W Cycle 1; 100 mg/m ² Q2W Cycle 2 and thereafter	8 mg/kg Q2W
Minus -1 (DL -1)	150 mg/m ² Q2W Cycle 1; 100 mg/m ² Q2W Cycle 2 and thereafter	8 mg/kg Q2W

BSA = body surface area; DL -1=dose level -1; Q2W = every 2 weeks.

Infusion of tusamitamab ravtansine will be administered at least 1 hour after the end of ramucirumab infusion for at least the first 2 cycles. For participants with a BSA >2.2 m², the tusamitamab ravtansine dose will be calculated based on a BSA of 2.2 m².

As no overlap in the safety profiles for ramucirumab and tusamitamab ravtansine is anticipated, the starting dose for tusamitamab ravtansine is selected as the maximum tolerated dose (MTD) used in studies evaluating tusamitamab ravtansine as loading-dose monotherapy. Enough participants will be enrolled in Part 1 to achieve 6 to 12 participants evaluable for DLTs to confirm the recommended dose. The tolerability of the combination is assessed in Part 1 according to the algorithm illustrated in Figure 1. The DLT observation period is the first 2 cycles (approximately 28 days). A DLT-evaluable participant must have completed 2 cycles of treatment or have been discontinued from study treatment because of a DLT; DLT-nonevaluable participants will be replaced. A minimum delay of 1 week is required between the initial dose in the first participant treated in a DL cohort and dosing of the next 2 participants treated at the same DL.

Figure 4 Decision tree for tusamitamab ravtansine leading dose in Part 1

Note: Abbreviations: DL -1 = dose level -1 (150 mg/m²); DLT = dose-limiting toxicity.
In case of 2 or more DLTs at DL-1, an alternative dosage may be considered or the study may be stopped.

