Any patient who has had 1 tusamitamab ravtansine dose reduction or 2 ramucirumab dose reductions and who experiences an event that would cause an additional dose reduction must be discontinued from tusamitamab ravtansine/ramucirumab.

If 1 of the 2 drugs (tusamitamab ravtansine or ramucirumab) is prematurely permanently discontinued, the other drug can be continued until disease progression.

Retreatment of a patient requiring a dose delay of more than 1 month will need to be justified by an individual case risk-benefit assessment.

6.5.1 Retreatment criteria: Part 1 and Part 2

All participants entered into the study will be treated at Day 1. A participant may receive additional study interventions if he/she meets retreatment criteria as determined by the Investigator and agrees to be retreated.

At Day 1, the participant must meet all of the following criteria to be eligible for retreatment:

- Neutrophil count $\geq 1.5 \times 10^9/L$.
- Platelets $\geq 100 \times 10^9/L$.
- Total bilirubin $\leq 1.5 \times ULN$.
- AST, ALT $\leq 2.5 \times ULN$ or $\leq 5 \times ULN$ in case of documented liver metastasis.
- No IMP-related toxicity Grade >1 (except for alopecia) or baseline severity.

- Urine protein:
 - <2+ on dipstick or urinalysis for C1D1
 - ≤2+ on dipstick or urinalysis for subsequent infusions
- OR
- <2 g on 24 hour urine collection.
- Hypertension is controlled. Every attempt should be made to control blood pressure (<150 mmHg systolic and <90 mmHg diastolic).
 - Wound healing: any wound is fully healed.

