9.2 POPULATIONS FOR ANALYSES

The following populations for analyses are defined in [Table 9](#):

Table 9 - Populations for analyses

Population	Description
Prescreened	All participants who signed the prescreening informed consent for CEACAM5 assessment of their biopsy.
Screened	All participants who signed screening informed consent for study participation.
Enrolled	Participants from screened population who have been allocated to intervention regardless of whether the intervention was received or not.
All-treated	All enrolled participants exposed to the study treatment, regardless of the amount of treatment administered. This population is the primary population for all efficacy parameters.
DLT-Evaluable (Part1)	All enrolled participants who received 2 cycles with at least 80% of the intended dose for both tusamitamab ravtansine and ramucirumab at each of the first 2 infusions unless they discontinued the study intervention before the end of Cycle 2 due to a DLT.
Activity	All treated participants who have measurable disease at study entry and at least 1 postbaseline evaluable tumor assessment. Participants with no postbaseline evaluable tumor assessment but with an early clinical progression or who died from disease progression will also be included in this set. This population is the secondary population for all efficacy parameters.
PK	All participants from the all-treated population with at least 1 postbaseline PK concentration (whatever the cycle and even if dosing is incomplete) with adequate documentation of dosing and sampling dates and times.
ATA	All participants from the all-treated population with at least 1 postbaseline ATA result (negative, positive or inconclusive).

Abbreviations: ATA = antitherapeutic antibody; CEACAM5 = carcinoembryonic antigen-related cell adhesion molecule 5; DLT = dose-limiting toxicity; PK = pharmacokinetic.

Participants exposed to study intervention before or without being enrolled will not be considered enrolled and will not be included in any analysis population. The safety experience of these participants will be reported separately.

Enrolled participants for whom it is unclear whether they took the study intervention will be considered as exposed and will be included in the safety population.

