# 4 SAMPLE SIZE DETERMINATION

The safety run-in (Part 1) aims to confirm the recommended dose of tusamitamab ravtansine loading dose Q2W in combination with ramucirumab according to DLTs observed.

Part 2 of this study is designed to obtain preliminary efficacy, safety, and PK data on tusamitamab ravtansine loading dose Q2W administered in combination with ramucirumab to participants with gastric or GEJ adenocarcinoma. As Part 2 is not intended to explicitly test a hypothesis, calculations of power and Type I error were not considered in the study design.

Assuming a prescreening failure rate of 70% and a study screen failure rate of 20%, approximatively 158 participants will be prescreened to achieve up to approximatively 38 treated participants in the safety run-in (Part 1) and Part 2.

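### The SAP's operational rule for the DLT-evaluable set omits the 80% minimum-dose criterion that SAP Table 4 and protocol Table 9 require of participants without a DLT

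*SAP*

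**What the plan says.** Four places bear on who is DLT-evaluable.

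- **SAP Table 4 (Section 2)** asks the following of anyone without a DLT: "received 2 cycles with at least 80% of the intended dose for both tusamitamab ravtansine and ramucirumab at each of the first 2 infusions". It then adds an exception that applies whatever the dose: "Any participant who experienced a DLT during that period will also be DLT-evaluable".
- **Protocol Table 9 (Section 9.2)** sets the same limit: "received 2 cycles with at least 80% of the intended dose for both tusamitamab ravtansine and ramucirumab". It too applies the limit to both infusions, except for those who stopped before the end of Cycle 2 because of a DLT.
- **The 'In practice' paragraph of SAP Section 2** includes a participant when the DLT eCRF page is filled in at the end of both cycles (Cycle 1 alone if a DLT prevented Cycle 2). It continues: "This includes any participant followed up to the end of the DLT observation period", or with a DLT validated by the Study Committee. It excludes overdoses of 30% or more above the intended dose at either infusion. It gives no lower dose limit.
- **Protocol Sections 1.1 and 4.1**, where replacement of nonevaluable participants is stated, say: "A DLT-evaluable participant must have completed 2 cycles of treatment or have been discontinued from study treatment because of a DLT". No 80% limit appears there.

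Protocol Section 9.3.2.1 makes the DLT-evaluable population the analysis set for the Part 1 primary endpoint. SAP Section 4 expects around 6 to 12 such participants.

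**The concern.** The SAP defines the set one way and then gives a rule for building it that yields a different set. The difference is one-sided. A participant with a DLT is counted under either text, so the conflict over the minimum dose affects only participants without a DLT. Those who received too little of either drug would be added to the denominator as having tolerated the combination.

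The protocol's own instructions can lead there. Section 6.5 says that if one of the two drugs "is prematurely permanently discontinued, the other drug can be continued until disease progression". Appendix 6 directs permanent discontinuation of tusamitamab ravtansine for some events that protocol Table 6 does not automatically class as DLTs, for example a Grade 3 infusion reaction, Grade 3 neuropathy or a Grade 2 or 3 conduction disorder. It directs omission of ramucirumab for marked proteinuria. Such a participant can reach Cycle 2 Day 14 on one drug with both DLT pages completed.

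The estimand is also touched. Protocol Section 9.3.2.1 sets no intercurrent-event strategy, on the ground that members of this set will not discontinue intervention before a DLT or the end of Cycle 2. If stopping one drug counts as discontinuation, the operational rule removes that ground.

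**Working it through.** The plan gives no figure for the effect of this rule, so there is none to reproduce. The check sets the rules side by side and then illustrates the size.

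**Who is in the set.** Each participant below has no DLT, has both DLT pages completed and is followed to Cycle 2 Day 14. Dose steps are from protocol Table 7.

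| Dosing in the first 2 cycles | SAP Table 4 / protocol Table 9 | 'In practice' rule |
|---|---|---|
| Both drugs at 80% or more, both infusions | in | in |
| Tusamitamab ravtansine stopped for good in Cycle 1, ramucirumab continued | out | **in** |
| Ramucirumab omitted at Cycle 2, tusamitamab ravtansine given | out | **in** |
| Ramucirumab 6 mg/kg at Cycle 2 | out if intended means starting dose (6/8 = 75%); in if it means modified dose (6/6 = 100%) | in |
| Tusamitamab ravtansine 80 mg/m² at Cycle 2 | in (80/100 = 80%) | in |
| Either drug overdosed by 30% or more | not excluded | **out** |

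The operational rule departs from the tables in both directions: it drops the lower limit and adds an upper one.

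**Size.** Let n be the number counted by the operational rule, d the number with a DLT, and k the number under-dosed without a DLT. The documents give no value for k; it is assumed here. The reported incidence is d/n. Under Table 4, before any replacement, it is d/(n − k).

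| n | d | k = 0 (as reported) | k = 1 | k = 2 |
|---|---|---|---|---|
| 6 | 1 | 1/6 = 16.7% | 1/5 = 20.0% | 1/4 = 25.0% |
| 6 | 2 | 2/6 = 33.3% | 2/5 = 40.0% | 2/4 = 50.0% |
| 12 | 1 | 1/12 = 8.3% | 1/11 = 9.1% | 1/10 = 10.0% |
| 12 | 2 | 2/12 = 16.7% | 2/11 = 18.2% | 2/10 = 20.0% |

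Whenever d and k are both above zero, the reported figure is too low. With d = 0 the rate is 0% either way and only the denominator is overstated. The shifts are small beside the sampling error: exact 95% intervals are 0.4% to 64.1% for 1/6, 0.5% to 71.6% for 1/5 and 0.6% to 80.6% for 1/4.

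**The case against.** The strongest reply is that Table 4 still governs and the operational paragraph works inside it. The 'In practice' text for the activity population adds exclusions without restating Table 4, and the version history calls the change to the DLT-evaluable definition a clarification. The eCRF instructions, which are not in these documents, might restrict the DLT page to adequately dosed participants. This reading is possible, but the SAP does not state it. The wording of the follow-up sentence covers everyone followed, which fits poorly with an 80% floor. The parallel 'In practice' rule for the enrolled population works as a complete inclusion rule.

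It is also fair to say that under-dosing without a DLT may be rare. Grade 1-2 infusion reactions may be resumed, the SAP sums the portions given, and any event may be deemed dose limiting. Protocol Table 2 reports 1 Grade 3 hypersensitivity event among 160 pooled monotherapy patients. If that rate carried over, the chance of at least one would be 1 − (159/160)^6, about 4%, in 6 participants, and about 7% in 12. That stands for that route, but it is only one of several.

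A third reply is that under-dosing would be visible in the outputs. This holds only in part. Dose modifications are tabulated for the all-treated population by dose level, and the DLT listing shows DLTs, so neither identifies an under-dosed participant without a DLT in the evaluable set.

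Two stronger readings are tempting. A reader might infer that the SAP has no dose check at all. It has one, for overdose, and Table 4 itself carries the 80% limit. A reader might also infer that the rule makes it easier to carry an intolerable loading dose into Part 2. The documents do not support that: the Figure 1 decision tree is not shown, the Study Committee takes the decision, nothing shows that it uses this SAP set, and the affected infusion may be either drug at either cycle rather than the loading dose.

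**Conclusion.** The point holds as a conflict between the formal definition of the DLT-evaluable set and the rule for building it. The operational rule has no minimum-dose check. Taken literally, it admits participants whom SAP Table 4 and protocol Table 9 exclude, and the resulting error in DLT incidence can only be downward.

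The size depends on how many such participants occur. With 1 DLT among 6 counted, one under-dosed participant means 16.7% is reported instead of 20%, and two mean 16.7% instead of 25%. With none, there is no effect. These figures assume k and take the excluded participants as not yet replaced. Part 1 tests no hypothesis, so what is at risk is a descriptive estimate, though it is the Part 1 primary endpoint. No effect on the dose decision can be computed from the documents.

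**What to change.** Reconcile the 'In practice' paragraph with SAP Table 4 and protocol Table 9:

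1. Derive the set from the exposure data. Include participants who meet the 80% criterion already defined, for both drugs at each of the first 2 infusions, and have DLT pages completed at the end of Cycles 1 and 2; or who have a Study Committee-validated DLT.
2. Delete the sentence on participants followed to the end of the observation period, or make it subject to the 80% criterion.
3. State whether intended dose means the starting dose or the dose after a protocol-directed modification. A ramucirumab step to 75% of the starting dose turns on this.
4. Align the evaluability and replacement wording in protocol Sections 1.1 and 4.1 with Section 9.2.

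The cost is a wording change and one derivation; actual dose per drug is already computed under SAP Sections 3.6.1.2 and 3.6.1.3. The downside is that the evaluable set may be smaller by a participant or two.
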